9.6.2.3 Common TEAEs

TEAEs with subject incidence $\geq 5\%$ (or another cut-off if justified) in any treatment group will be summarized by SOC and PT as well as by PT only in descending order of subject incidence.

9.6.2.4 Drug-related TEAEs

Drug-related TEAEs will be summarized and new events of drug-related TEAEs by exposure interval will be summarized.

9.6.2.5 TEAEs by Maximum Severity

All TEAEs will be summarized by maximum severity (mild, moderate, severe, and, if needed, missing). If a subject reports multiple occurrence of a specific event within a specific analysis phase or period, the subject will be counted only once by the maximum severity. If the severity is missing for one or more of the occurrences, the maximum severity of the remaining occurrences will be used. If the severity is missing for all the occurrences, the subject will be counted only once in the “missing” category of severity.

9.6.2.6 Serious TEAEs

Serious TEAEs and serious drug-related TEAEs will be summarized.

New events of serious TEAEs and serious drug-related TEAEs by exposure interval will be summarized for Placebo-controlled Phase (Weeks 0 to 16).

Serious TEAEs will be summarized by age category (< 65, ≥ 65 years), sex and race.

A subject data listing of all serious AEs (both TEAEs and non-TEAEs) will be provided.

9.6.2.7 TEAEs Leading to Drug Interruption and Drug Withdrawal

TEAEs leading to drug interruption and TEAEs leading to drug withdrawal will be summarized.

TEAEs leading to drug withdrawal will also be summarized by age category (< 65, ≥ 65 years), sex and race.

A subject data listing of TEAEs leading to drug withdrawal will be provided.

9.6.2.8 Deaths

TEAEs leading to death will be summarized. A subject data listing of all deaths will be provided.

9.6.2.9 Adverse Events of Special Interests

Summary tables and listings may be provided for the AESIs if deemed necessary.

9.6.3 Laboratory Test Results

The endpoints for clinical laboratory evaluations include:

- Laboratory marked abnormalities
- Observed value and change from baseline over time in the following laboratory parameters including but not limited to
 - Complete blood count: red blood cell [RBC] count, hemoglobin, hematocrit, white blood cell [WBC] count and differential, absolute WBC counts, platelet count
 - Serum chemistry: total protein, albumin, calcium, phosphorous, glucose, total cholesterol [TC], triglycerides, high-density lipoprotein [HDL], high-density lipoprotein cholesterol [HDL-C], low-density lipoprotein cholesterol [LDL-C], uric acid, total bilirubin, alkaline phosphatase, aspartate aminotransferase [AST; serum glutamic-oxaloacetic transaminase, SGOT], alanine aminotransferase [ALT; serum glutamic pyruvic transaminase, SGPT], sodium, potassium, chloride, bicarbonate [carbon dioxide, CO₂], blood urea nitrogen, creatinine, lactate dehydrogenase [LDH], and magnesium
 - Dipstick urinalysis: specific gravity, pH, glucose, ketones, protein, blood, bilirubin, leukocyte esterase, nitrite, and urobilinogen

- Shifts from baseline to post-baseline time points and to the worst post-baseline value in terms of normal/abnormal (low or high) in the above hematology and serum chemistry parameters

Summary statistics of observed values and changes from baseline in laboratory parameters will be provided over time. Frequency summaries (shift tables) of shifts from baseline to post-baseline time points and to the worst post-baseline value in terms of normal/abnormal will be provided.

9.6.4 Vital Signs

The endpoints for vital signs include:

- Observed value and change from baseline over time in vital signs (temperature, pulse, and blood pressure)
- Shifts from baseline to post-baseline time points and to the worst post-baseline value in terms of normal/abnormal in pulse and blood pressure (normal ranges are defined as: 60-100 beats/minute for pulse, 90-140 mmHg for systolic blood pressure, and 60-90 mmHg for diastolic blood pressure)

Summary statistics of observed values and changes from baseline in vital signs will be provided over time. Frequency summaries (shift tables) of shifts from baseline to post-baseline time points and to the worst post-baseline value in terms of normal/abnormal will be provided for pulse and blood pressure.

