9.7. Safety Analysis

The safety analyses will be performed using the safety population, defined as all subjects who are randomized and receive at least one dose of investigational product. Safety will be assessed by clinical review of all relevant parameters including treatment-emergent adverse events (TEAEs), laboratory tests, and vital signs; no inferential testing for statistical significance will be performed. Data from safety assessments will be summarized descriptively for the Placebo-controlled Phase (Weeks 0 to 16) and the Apremilast Exposure Period when subjects receive apremilast treatment. For safety analyses in the Placebo-controlled Phase, baseline will be relative to the first dose date following randomization at Week 0. For safety analyses in Apremilast Exposure Period, baseline will be relative to the first apremilast dose date at Week 0 for subjects initially randomized to apremilast or Week 16 for subjects initially randomized to placebo and switched to apremilast in the Apremilast Extension Phase (Weeks 16-32).

Adverse events will be classified using the Medical Dictionary for Regulatory Activities (MedDRA) classification system. All TEAEs will be summarized by system organ class, preferred term, severity and relationship to investigational product. TEAEs leading to death or to discontinuation from treatment and serious adverse events will be summarized and listed separately.

Data from other safety assessments will be summarized descriptively. Shift tables for laboratory parameters showing the number of subjects with values low, normal, and high comparing with the normal reference ranges pre-treatment versus post treatment will be provided.

To account for the different exposure to the investigational product, adverse events or marked laboratory abnormalities will also be summarized using the exposure adjusted incidence rate, in addition to the simple incidence rates.

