5.2.3 Vital Signs and Weight

Vital signs and weight endpoints include:

- Observed value and change from baseline over time in vital signs (temperature, pulse, and blood pressure)
- Shifts from baseline to post-baseline time points and to the worst post-baseline value in terms of normal/abnormal in pulse and blood pressure (normal ranges are defined as: 60-100 beats/minute for pulse, 90-140 mmHg for systolic blood pressure, and 60-90 mmHg for diastolic blood pressure)
- Observed value, change and percent change from baseline over time in weight

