Descriptive statistics will be provided for vital signs, weight, height and BMI, laboratory values (continuous measurements) by treatment and visit, including the end of treatment visits. The baseline value, value at the time point, and change from baseline will be summarized for subjects who have values at baseline and at the time point.

Shift tables, that is, tables that summarize the baseline categories (normal, abnormal) versus the category at the end of the respective periods or versus the worst post-

baseline category, include subjects who have values at baseline and at least one post-baseline value. Similarly, in frequency summaries of shifts from baseline at scheduled study weeks per protocol, only subjects who have values at baseline and at the time point will be included.

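### The pulse and blood-pressure shift tables are defined as normal/abnormal against two-sided ranges, so a one-directional change in who leaves the range can be hidden

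*SAP*

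**What the plan says.** SAP 5.2.3 and 9.6.4 both give two-sided normal ranges: "60-100 beats/minute for pulse, 90-140 mmHg for systolic blood pressure, and 60-90 mmHg for diastolic blood pressure". The endpoint in 5.2.3 is "Shifts from baseline to post-baseline time points and to the worst post-baseline value in terms of normal/abnormal in pulse and blood pressure", and 9.6.4 repeats it (shifts "to the worst post-baseline value in terms of normal/abnormal in pulse and blood pressure") and plans frequency tables on that basis. Neither section names a direction for an abnormal value or defines the worst value.

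SAP 9.6.1 describes shift tables in general as "tables that summarize the baseline categories (normal, abnormal) versus the category at the end of the respective periods", or versus the worst post-baseline category.

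Laboratory shifts are worded differently. SAP 9.6.3 defines them "in terms of normal/abnormal (low or high) in the above hematology and serum chemistry parameters", and SAP 5.2.4 also carries the qualifier. Protocol 9.7 asks for "Shift tables for laboratory parameters showing the number of subjects with values low, normal, and high". It has no matching requirement for vital signs, which fall under safety data to be summarised descriptively.

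SAP 9.6.4 also plans summary statistics of observed values and change from baseline in vital signs over time.

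**The concern.** A range with two limits has two ways to be abnormal. If both go into one category, three things follow.

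- A subject who is low at baseline and high afterwards (or the reverse) counts as abnormal to abnormal, which is no shift.
- A one-directional drug effect moves some subjects out of the range at one end and others into it at the other. The abnormal count shows only the net of the two.
- The worst value has no clear meaning when both extremes are possible.

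At stake is how readable the safety tables are. The shift tables are the only planned categorical summary of pulse and blood pressure: the marked-abnormality criteria in SAP Appendix B cover laboratory analytes only, and the electrocardiogram section is not applicable. Protocol 9.7 assesses safety by clinical review, names vital signs, and plans no inferential testing. The reviewer therefore depends on what these tables display.

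**Working it through.** The plan states no figure that depends on the table categories, so there is nothing to reproduce. The check asks whether netting of the two tails can hide a shift, and whether it always does.

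**Inputs from the documents.** Limits: pulse 60 and 100, systolic 90 and 140, diastolic 60 and 90 (SAP 5.2.3, 9.6.4). Three post-baseline vital-sign visits in the Placebo-controlled Phase: Weeks 4, 8 and 16 (Protocol Table 3). About 143 subjects per arm (SAP 3.2).

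**Assumed inputs.** Means, SDs, drug shifts and within-subject correlation. The documents give none, so ranges are shown.

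**Single visit.** With values normal with mean m and SD s, low = Φ((lower − m)/s), high = 1 − Φ((upper − m)/s), and pooled abnormal = low + high.

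- Pulse, m = 72, s = 10. Low = Φ(−1.2) = 11.51%, high = 1 − Φ(2.8) = 0.26%, pooled 11.8%. After a rise of 5: low = Φ(−1.7) = 4.46%, high = 1 − Φ(2.3) = 1.07%, pooled 5.5%. High values rise while the pooled count roughly halves.
- Pulse, m = 80, s = 10. Low = high = Φ(−2) = 2.28%, pooled 4.6%. After a rise of 5: low = Φ(−2.5) = 0.62%, high = 1 − Φ(1.5) = 6.68%, pooled 7.3%. Here the pooled count rises.
- Systolic, m = 126, s = 15. Low = Φ(−2.4) = 0.8%, high = 1 − Φ(0.933) = 17.5%, pooled 18.4%. After a fall of 5: low = Φ(−2.067) = 1.9%, high = 1 − Φ(1.267) = 10.3%, pooled 12.2%.

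**Worst of three readings, diastolic.** Simulation of 400,000 subjects, SD 10, within-subject correlation 0.6, true fall of 5. A subject is low if any of the three readings is below 60, high if any is above 90, and pooled abnormal if either holds.

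| Assumed mean | Any low, no effect → fall of 5 | Any high | Pooled abnormal |
|---|---|---|---|
| 74 | 17.0% → 34.2% | 11.9% → 4.3% | 28.9% → 38.5% |
| 76 | 12.1% → 26.5% | 16.8% → 6.6% | 28.9% → 33.1% |
| 78 | 8.2% → 19.8% | 23.0% → 9.9% | 31.1% → 29.7% |
| 80 | 5.4% → 14.4% | 30.2% → 14.2% | 35.6% → 28.6% |

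In every row the low count at least doubles. The pooled count rises, stays nearly flat or falls according to how much of the starting distribution lies above 90.

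**In subjects.** At mean 78 with 143 per arm, low readings go from 143 × 0.082 ≈ 12 to 143 × 0.198 ≈ 28 subjects. Pooled abnormal goes from 143 × 0.311 ≈ 44 to 143 × 0.297 ≈ 42. This assumes that every subject has all three readings.

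**Mechanism.** Only about 0.02% of simulated subjects had both a low and a high post-baseline reading. The masking comes from exchange between the two tails across the group, hardly at all from individuals who swing from one extreme to the other.

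**The case against.** **Pooling is inferred.** The SAP never says that low and high are combined. It also uses normal/abnormal as shorthand where direction is kept: the closing sentence of 9.6.3 drops the qualifier for laboratory tables that 9.6.3 itself defines as low or high. The general wording in 9.6.1 covers those laboratory tables too, so it cannot prove that vital signs are pooled. The table shells are not in the documents and could show three categories without contradicting the text. This stands as far as it goes: the defect is in what is written, not in a known table. But neither vital-sign section carries the qualifier anywhere, and the worst value is left undefined.

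**Direction appears elsewhere.** A uniform shift is exactly what mean change by visit shows, and low blood pressure or fast pulse reported as adverse events would appear by preferred term. This also stands in part. Neither output counts the subjects who crossed each limit.

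**Some illustrations are small in subjects.** Pulse above 100 going from 0.26% to 1.07% is about 0.4 to 1.5 subjects of 143, and systolic below 90 going from 0.8% to 1.9% is about 1 to 3. Three categories could not separate changes of that size from chance. Only the diastolic example is sizeable, and at mean 78 its pooled count is nearly flat, not clearly lower.

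**Two stronger readings are not supported.** A reader might infer that a one-directional effect will always lower the abnormal count. The rows at means 74 and 76, and pulse at mean 80, show the reverse. A reader might also infer that the SAP departs from the protocol. It does not, because the protocol asks for low/normal/high for laboratory parameters only.

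**Conclusion.** The point holds as a minor safety-reporting improvement. SAP 5.2.3 and 9.6.4 set two-sided ranges, define shifts without direction, and leave the worst value undefined. Taken literally, the tables can hide a one-directional change in the number of subjects outside the range, and in some settings show it as fewer abnormal subjects. Whether they would do so here depends on which tail holds more subjects at baseline, which the documents do not say.

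Under the assumed diastolic distribution with mean 78, the share below 60 goes from 8% to 20% while pooled abnormal goes from 31% to 30%. At mean 76, pooled abnormal goes from 29% to 33%. These are illustrations resting on assumed normality, SD 10, correlation 0.6 and a fall of 5. They are not predictions for apremilast.

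Safety is descriptive. No hypothesis test, error rate, sample size or efficacy result is touched, and the underlying readings are kept, so the split could still be produced later.

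**What to change.** In SAP 5.2.3 and 9.6.4, define the shift categories for pulse, systolic and diastolic pressure as low, normal and high against the ranges already given. Adjust the general shift-table wording in 9.6.1 to match. Replace the single worst-value table with two per parameter: baseline category to lowest post-baseline category, and baseline category to highest post-baseline category.

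The cost is a few words in the SAP, revised table shells and slightly larger tables. No new data are needed. It is best settled before the Week 16 database is unblinded, when SAP section 1 requires the plan to be final.

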9.6.5 Physical Measurements

The endpoints for physical measurements are Observed value, change and percent change from baseline over time in weight. Summary statistics of will be provided over time. Frequency summaries of change and percent change in weight from baseline to the end of the period will be provided by baseline BMI category (< 25, \geq 25 to < 30, \geq 30 to < 35, \geq 35 to < 40, and \geq 40 kg) and by baseline weight category (< 70, \geq 70 to < 85, \geq 85 to < 100, and \geq 100 kg). The categories of weight change (kg) and percent change (%) are < -20, \geq -20 to < -10, \geq -10 to < -5, \geq -5 to < 0, 0, $>$ 0 to \leq 5, $>$ 5 to \leq 10, $>$ 10 to \leq 20, and $>$ 20. The end-of-period or end-of-phase value is the last post-baseline value in the analysis period or phase (excluding the value obtained at the follow-up visit, if applicable) up to 28 days after the last dose of IP in the study.

9.6.6 Electrocardiogram

Not applicable.

9.6.7 Antibody Formation

Not applicable.

9.6.8 Exposure to Investigational Product

Descriptive statistics will be produced to describe the exposure to investigational product by treatment group. Compliance to each IP will also be summarized.

The treatment compliance (in %) for each subject will be computed as 100 times the total number of tablets taken (the total number of tablets dispensed minus the total number of tablets returned) over the analysis phase or period divided by the intended total number of tablets that should have been taken over the same phase or period.

Summary statistics for compliance (%) will be provided by treatment arm for each analysis phase or period. Frequency summary tables of compliance will also be presented with the following categories: < 75%, $\geq 75\% - \leq 120\%$, and $> 120\%$. A subject data listing of drug accountability records will be provided.

9.6.9 Exposure to Non-investigational Product

Not applicable.

9.6.10 Exposure to Other Protocol-required Therapy

Not applicable.

9.6.11 Exposure to Concomitant Medication

The number and proportion of subjects receiving therapies of interest will be summarized by preferred term or category for each treatment group as coded by the World Health Organization Drug (WHODRUG) dictionary.

9.7 Other Analyses

[figure not shown]
9.7.1 Analyses of COVID-19 impacted data

Analyses will be performed to assess the impact of COVID-19 on the amount of data collected for the study. These analyses include:

- Number and percent of subjects who are discontinued treatment/study due to COVID-19
- Number and percent of subjects with important protocol deviations and protocol deviations related to COVID-19
- Analysis of the primary endpoint and key secondary endpoints excluding COVID-19 impacted subject data

- Number and percent of subject study participation impacted by COVID-19 along with the listing
- Listing of subject efficacy related assessment impacted by COVID-19

Listing of subject safety related assessment impacted by COVID-19

[figure not shown]

[figure not shown]
9.7.3 Analyses of Clinical Outcome Assessments

Not applicable.

9.7.4 Analyses of Health Economic Endpoints

Not applicable.

Appendix A. Analytical Windows

Post baseline time points in all analyses will be captured based on analysis visit window (range of study days) around the target day for each analysis visit, based on the actual day of evaluation relative to a reference date. Appropriate dates will be used to calculate the study day, e.g., date of measurement or date of specimen collection will first be used, and then the date of visits/study weeks as recorded in the database will be used.

Table 4. Table for Visit Mapping for by Time Point Analysis

Analysis Visit	Target Day	Visit Window (Days)
Week 0 (Baseline)	1	≤ 1
Placebo-controlled Phase		
Week 2	15	2 – 21
Week 4	29	22 – 42
Week 8	57	43 – 70
Week 12	85	71 – 98
Week 16	113	99 – End of Phase
Apremilast Extension Phase		
Week 20	141	Start of Phase – 154
Week 24	169	155 – 196
Week 32	225	197 – End of Phase

Note: Target day and visit window are relative to the date of Visit 2/Week 0 (Day 1) randomization date. For efficacy and safety analysis, definitions for start or end dates for a phase or period are specified in [Section 3.1](#) and Baselines are specified in [Section 5.4](#). For endpoints that do not have week 12 assessment, the visit window for week 8 will be 43 – 98 (Days).

Time points in the analyses or summaries of efficacy data over time include the scheduled study weeks per protocol, the end of a study phase, and the observational follow-up visit when applicable. Appropriate dates (e.g., date of measurement or date of specimen collection) will first be used to ensure only data (including data from scheduled, unscheduled, discontinuation, and observational follow-up visits) measured or collected within the specific analysis phase (as defined in [Section 3.1](#)) being analyzed or summarized are included, and then the visits/study weeks as recorded in the database will be used to assign one value (possibly missing) to each time point at the

subject level. It is possible that multiple assessment values will fall into the same visit window. The following rule may be used to select the unique value for that analysis visit:

1. Among all assessments in the same visit window for the analysis visit, select the value with the assessment date closest to the target day of the analysis visit;
2. If the relative days from 2 assessments are equally close to, but on different sides of the target day, then the latter assessment will be used for that analysis visit;
3. If multiple assessments are available on the same relative day, then the highest value of these assessments will be used for that relative day.

For the Apremilast-exposure Period, the study weeks relative to the first dose of apremilast (according to the baseline definition) for placebo subjects who are treated with apremilast 30 mg BID starting at Week 16/Visit 7 are shown below for summaries of safety data (laboratory parameters, vital signs, etc) over time.

Table 5. Analysis Visit for Placebo Subjects Who Are Treated with Apremilast 30 mg BID after Week 16 in the Apremilast-exposure Period

Original Visit	Analysis Visit for subjects initially randomized to placebo
Week 16	Week 0 (Baseline)
Week 20	Week 4
Week 24	Week 8
Week 32	Week 16

Data collected in the observational Follow-up Phase will be summarized separately when applicable.

Appendix B. Laboratory Marked Abnormalities Criteria

Category / Analyte	SI Units	Criteria
Chemistry/ Alanine Aminotransferase (SGPT)	U/L	> 2*ULN
Albumin	Kg/m3	< 25
Alkaline Phosphatase	U/L	> 400
Aspartate Aminotransferase (SGOT)	U/L	> 2*ULN
Total Bilirubin	µmol/L	> 2*ULN
Total Bilirubin and Alanine Aminotransferase /Aspartate Aminotransferase	µmol/L and U/L	Bilirubin Value > 2xULN with (ALT or AST value > 2xULN)
Blood Urea Nitrogen	mmol/L	> 24
Calcium	mmol/L	< 1.8 > 3.0
Cholesterol	mmol/L	> 7.8
Creatinine	µmol/L	> 1.5*ULN
Glucose	mmol/L	< 2.8 > 13.9
Hemoglobin A1C	%	> 6.5
Lactate Dehydrogenase (LDH)	U/L	> 2*ULN
Magnesium	mmol/L	> 1.2
Phosphate	mmol/L	<1.03 >1.94
Potassium	mmol/L	<3.0 >5.4
Sodium	mmol/L	<132 >147
Triglycerides	mmol/L	> 3.4
Urate	umol/L	Male: > 480 Female: > 480
Hematology/ Hemoglobin	g/L	Female <110, Male <110 Female >150, Male >150
Leukocytes	10^9/L	< 2.0
Lymphocytes	10^9/L	< 1.0
Neutrophils	10^9/L	< 1.5
Platelets	10^9/L	<100 >500

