5.2.4 Clinical Laboratory Evaluations

Laboratory evaluations include:

- Observed value and change from baseline over time in hematology and serum chemistry parameters
- Laboratory marked abnormalities and by baseline laboratory category will be analyzed for selected analytes ([Appendix B](#)).
- Shifts from baseline to post-baseline time points and to the worst post-baseline value in terms of normal/abnormal (low or high) in hematology and serum chemistry parameters

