7.4.1 Analysis Phases

Per protocol specification, data summary and analysis will be provided for the following phases:

7.4.1.1 Placebo-controlled Phase – Weeks 0 to 16

This phase starts on the day of randomization (Week 0/Visit 2), and stops on either: (1) the day the first IP for the next phase is dispensed at Week 16/Visit 7; or (2) the day of the discontinuation visit if the subject discontinued prior to or at Week 16/Visit 7; or (3) the last known study day if the subject is lost to follow-up prior to Week 16/Visit 7 during the phase.

For safety analysis in subjects who continued treatment in Apremilast Extension Phase (Weeks 16 to 32), the phase stopped one day prior to the first dose date in Apremilast Extension Phase.

For analysis of adverse events, TEAEs in the phase including those with start date at the first IP dose date through either: (1) one day prior to the first IP dose date in Apremilast Extension Phase (Weeks 16 to 32); or (2) 28 days after the last IP dose date for subjects who discontinue after only receiving treatment in the Placebo-controlled Phase.

For safety analysis of visit-based data (ie, laboratory parameters, vital signs, etc), the post-baseline data in the phase including those with assessments dates after the first IP dose date (exclusive) and through either: (1) the first IP dose date (inclusive) in Apremilast Extension Phase (Weeks 16 to 32); or (2) the last visit date within 28 days of the last IP dose date (prior to the first Follow-up Visit) for subjects who discontinue after only receiving treatment in the Placebo-controlled Phase.

At the time of the Week 16 analysis, if the date of the first IP dose date in Apremilast Extension Phase is not available in data base and the subject has not discontinued, the first IP dispensing date will be used instead.

7.4.1.2 Apremilast Extension Phase – Weeks 16 to 32

This phase starts on the day after the first IP is dispensed for the phase at Week 16/Visit 7, and stops on either: (1) the day of Week 32/Visit 10; or (2) the day of the discontinuation visit if the subject discontinued prior to or at Week 32/Visit 10; or (3) the last known study day if the subject is lost to follow-up prior to Week 32/Visit 10 during the phase.

For safety analysis, the phase started at the first dose date in the phase and ended at the last dose date.

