9.6 Safety Analyses

9.6.1 Analyses of Primary Safety Endpoint(s)

Safety will be assessed via descriptive statistics. Unless otherwise specified, all safety analyses described in this section will be performed for both the Placebo-controlled Phase and the Apremilast-exposure Period. The safety analyses for the Placebo-controlled Phase will be based on the safety population and presented by treatment group (placebo arm or apremilast arm), and the safety analyses for the Apremilast-exposure Period will be based on the apremilast subjects as treated population and

presented by treatment group (Placebo/30 mg BID, 30 mg BID as Initiated and 30 mg BID as Treated).

For the analyses of AEs and lab marked abnormalities, the following endpoints will also be summarized:

- Subject incidence: Subject incidence (i.e., percentage [%] used in a frequency summary) is defined as the number of subjects with the specific event divided by the number of subjects included in the analysis. Subjects with multiple occurrences of the specific event in the specific analysis period will be counted only once in the numerator.
- Exposure-adjusted incidence rate (EAIR) per 100 subject-years: The EAIR per 100 subject-years is defined as 100 times the number of subjects with the specific event divided by the total exposure time (in years) among subjects included in the analysis. Subjects with multiple occurrences of the specific event in the specific analysis period will be counted only once in the numerator. The exposure time for a subject without the specific event is the treatment duration, whereas the exposure time for a subject with the specific event is the treatment duration up to the start date (inclusive) of the first occurrence of the specific event. The total exposure time in years is calculated by dividing the sum of exposure time in days over all subjects included in the analysis by 365.25. The EAIR per 100 subject-years is interpreted as the expected number of subjects with at least one occurrence of the specific event per 100 subject-years of exposure to the IP.

AEs and lab marked abnormalities will be summarized by subject incidence and EAIR for the Placebo-controlled Phase (Weeks 0 to 16) and for the Apremilast-exposure Period. In addition, selected summaries for the Apremilast Extension Phase (Weeks 16 to 32) and the Observational Follow-up Phase (4 weeks) may be presented if deemed necessary.

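### SAP Appendix B can count in-range results as marked abnormalities (hemoglobin above 150 g/L in men, phosphate below 1.03 mmol/L), depending on the central laboratory's ranges

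*SAP*

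**What the plan says.** SAP Appendix B lists the criteria for laboratory marked abnormalities. Hemoglobin, in g/L, reads "Female <110, Male <110 Female >150, Male >150": laid out by sex, with the same numbers for both. Phosphate is flagged below 1.03 or above 1.94 mmol/L. Of the 24 rows, 6 are tied to the laboratory's own range: ALT, AST, total bilirubin, bilirubin combined with ALT or AST, creatinine and LDH. Each of these sits at 1.5 or 2 times ULN. The other 18 rows, including hemoglobin and phosphate, use fixed values.

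SAP 5.2.4 applies the list: "Laboratory marked abnormalities and by baseline laboratory category will be analyzed for selected analytes". SAP 9.6.1 reports the flagged subjects as incidence and as EAIR, for both the Placebo-controlled Phase and the Apremilast-exposure Period. Incidence "is defined as the number of subjects with the specific event divided by the number of subjects included in the analysis". Neither section adds the condition that the value be out of range.

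The shift tables use a different yardstick. Protocol 9.7 has them show the "number of subjects with values low, normal, and high comparing with the normal reference ranges". Laboratory work is done centrally (Protocol 6.5), but neither document states the reference ranges.

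**The concern.** Two safety displays classify the same result by different rules. The shift tables go by the laboratory's range and the marked-abnormality rows go by Appendix B. Where an Appendix B limit lies inside the range, one result is normal in the first display and a marked abnormality in the second.

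The SAP does not define a marked abnormality in words. Every row that refers to the laboratory's range nevertheless sets the threshold well outside it, so an in-range limit would sit badly with the rest of the table.

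What is at stake is the usefulness of two rows. If ordinary values from both arms are counted, the incidence and EAIR for that analyte mix them with real abnormalities, and a true signal is harder to see.

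**Working it through.** The plan gives no figure to reproduce here. The check is a logical condition followed by an illustration of size.

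**Condition.** Let U be the male hemoglobin ULN and L the phosphate LLN.
- If U ≤ 150, no in-range male value is flagged. If U > 150, every value above 150 and up to U is in range and flagged.
- If L ≥ 1.03, no in-range phosphate value is flagged. If L < 1.03, every value from L to just under 1.03 is in range and flagged.

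**Inputs for the illustration.** The limits 150 and 1.03 come from Appendix B. All reference ranges and the normal shape are assumptions.

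**Model.** Take the reference interval (LLN, ULN) as the central 95% of a normal distribution, so mean m = (LLN + ULN)/2 and SD s = (ULN − LLN)/3.92. The share of in-range values that is flagged is:
- hemoglobin: [0.975 − Φ((150 − m)/s)] / 0.95
- phosphate: [Φ((1.03 − m)/s) − 0.025] / 0.95

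**Worked cases.**
- Hemoglobin, range 130 to 160: m = 145, s = 30/3.92 = 7.65, (150 − 145)/7.65 = 0.653, Φ = 0.743. Share = (0.975 − 0.743)/0.95 = 0.232/0.95 = 24%.
- Phosphate, range 0.90 to 1.50: m = 1.20, s = 0.60/3.92 = 0.153, (1.03 − 1.20)/0.153 = −1.11, Φ = 0.133. Share = (0.133 − 0.025)/0.95 = 0.108/0.95 = 11%.

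**Results, hemoglobin in men (assumed LLN 130 throughout).**

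| Assumed ULN | Flagged and in range, of all men | Share of in-range men flagged |
|---|---|---|
| 150 | 0 | 0% |
| 155 | 0.095 | 10% |
| 160 | 0.232 | 24% |
| 170 | 0.475 | 50% |
| 180 | 0.627 | 66% |

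**Results, phosphate.**

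| Assumed LLN | Assumed ULN | Share of in-range subjects flagged |
|---|---|---|
| 1.03 | 1.50 | 0% |
| 1.00 | 1.40 to 1.50 | about 2% |
| 0.90 | 1.50, 1.45 | 11%, 13% |
| 0.80 | 1.45, 1.40 | 27%, 31% |

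**In subjects.** Assume 50% to 70% of each arm are men. At ULN 155, the in-range men flagged are at most 143 × 0.5 × 0.095 = 6.8 to 143 × 0.7 × 0.095 = 9.5 per arm. At ULN 160 the figures are 143 × 0.5 × 0.232 = 16.6 to 143 × 0.7 × 0.232 = 23.2. These are ceilings, because 143 assumes that every subject has a post-baseline sample. For those who discontinue, SAP 7.4.1.1 uses data up to "the last visit date within 28 days of the last IP dose date". A subject lost to follow-up may have no sample at all, and the plan assumes 20% dropout.

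These are single-sample rates. They suit the Placebo-controlled Phase, whose only scheduled post-baseline laboratory sample is at Week 16 (Protocol Table 3).

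**The case against.** The strongest objection is that no error has been shown. The ranges are not in the documents, and the illustration starts at 0%, so limits that are entirely in order fit everything that can be read. That stands, and the point can only be put conditionally.

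A second objection is that nothing singles out these two analytes. The same question could be asked of the sodium, potassium, lymphocyte or platelet limits. This also largely stands. Hemoglobin draws attention because it is listed by sex with one number for both, but phosphate has no such mark. It is a reason to prefer a rule that works whatever the ranges are, and it does not remove the gap in the counting rule.

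Third, other displays already separate normal from abnormal. Marked abnormalities are also analyzed by baseline laboratory category (SAP 5.2.4), shifts to the worst post-baseline value are tabulated (SAP 9.6.3), and laboratory values judged clinically important are recorded as adverse events (Protocol 10.3). These soften the harm but leave the incidence and EAIR rows as they are.

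Three stronger readings are tempting, and the documents support none of them:
- A reader might infer that the equal male and female hemoglobin limits are a copying slip. Urate has the same layout, "Male: > 480 Female: > 480", so a single limit for both sexes may be deliberate.
- A reader might infer that the limits are known to lie inside the normal range. Without the laboratory's ranges that cannot be said.
- A reader might infer that the safety comparison is biased. The same limits apply to both randomized arms, and Protocol 9.7 states that "no inferential testing for statistical significance will be performed".

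**Conclusion.** The point holds as a conditional one and is minor. As written, the SAP's counting rule lets an in-range result be reported as a marked abnormality if the male hemoglobin ULN is above 150 g/L or the phosphate LLN is below 1.03 mmol/L. Whether either condition is met cannot be settled from the documents.

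The size runs from nothing to a large part of the row: 0% to 66% of in-range men for ULN 150 to 180, and 0% to about 31% of in-range subjects for phosphate LLN 1.03 to 0.80. Those figures rest wholly on the assumed intervals and on normality. The consequence is limited to diluted descriptive rows for two analytes. There is no effect on efficacy, power or type I error, and no bias toward one arm.

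**What to change.** Before Week 16 unblinding, adopt one of two rules for the hemoglobin upper limit and the phosphate lower limit:

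1. Count the criterion only when the value is also outside the central laboratory's reference range, sex-specific where the laboratory gives one.
2. Compare each limit with that range and replace any limit found inside it with one tied to ULN or LLN, as 6 of the 24 rows already are.

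Neither rule alters any count if the limits already lie at or outside the range. The first needs no prior look-up, but where a limit is in range it reduces the criterion to any out-of-range value. The second keeps a distinct meaning for a marked abnormality. The first could be extended to the other fixed-limit rows in the same edit.

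The cost is a small change to the appendix and its programming, and some loss of comparability with any tables already programmed with these limits. Settling it before unblinding avoids changing a safety definition once the data have been seen.
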